7.6 Discussion of Risks as Part of the Consent Process

The study team will discuss all procedures, risks, and benefits with potential study participants, as part of the consent process. An IRB approved written informed consent document will be required for participation in this study. It is understood that consent is a process and not a discrete event. A participant's decision to withdraw consent will be respected throughout the duration of each subject's participation in this study. It is also understood that there may be as-yet unknown or unanticipated adverse effects of this study. The study team will continually monitor for these effects and consider altering the protocol as needed to ensure

patient safety. Changes in the procedures of the study, as well as any change(s) in the risks and/or benefits will be presented to and discussed with the subjects upon approval from the IRB for implementation of such revision(s), and any IRB revised written consent will be signed, as appropriate.

8.0 Reporting of Adverse Events or Unanticipated Problems involving Risk to Participants or Others

8.1 Adverse Events

8.2 Serious Adverse Events

8.2.1 Defining Serious Adverse Events

Consistent with FDA guidelines, serious adverse events (SAEs) will be defined as any untoward medical occurrence that:

- requires inpatient hospitalization
- results in persistent or significant disability
- is suspected to cause a congenital anomaly or birth defect in a subject's unborn child
- is life-threatening
- results in death
- is considered to be an important medical event based on appropriate medical judgement (e.g. bronchospasms requiring emergency department referral, seizures that might not result in hospitalization).

8.2.2 Assessing relationship between a SAE and relationship to study procedures

An SAE's relationship to the study procedures will be assessed and graded as either: not related, unlikely, possible, probable, or definite.

8.2.3 Assessing whether an AE is an anticipated problem

Any AE will be assessed for whether or not it was an anticipated problem. In accordance with Department of Health and Human Services guidance and consistent with 45 CFR part 46, an "unanticipated problem" will include any incident, experience, or outcome that meets all of the following criteria:

1. unexpected (in terms of nature, severity, or frequency) given
 - a. the research procedures that are described in the protocol-related documents, including the IRB-approved research protocol and informed consent document; and

- b. the characteristics of the subject population being studied; related or possibly related to participation in the research; and
2. suggests that the research places subjects or others at a greater risk of harm.
3. related or possibly related to participation in the research;
4. suggests that the research places subjects or others at a greater risk of harm than was previously known or recognized.

8.2.4 Unanticipated, non-serious AEs

All unanticipated, non-serious AEs and the study team's response to the non-serious AE will be included in a report at the time of annual continuing review. The PI will review the AEs and notify the Data Safety Monitor (DSM) and the IRB of any changes needed to the protocol. If needed, appropriate changes will be made to the consent form.

8.2.5 Unanticipated SAEs

In accordance with IRB policy, any unanticipated SAE that is considered possibly related to participation in the study will be reported within 7 calendar days of the PI's notification of the event to the IRB and DSM. The study team will continue to follow or obtain documentation of the resolution of any SAE.

8.2.6 Adverse Event Reporting

The annual summary of all unanticipated adverse events and any audit reports will be sent to the IRB at the time of continuing review. A copy of this report will also be sent to the NIH who will fund the PI on a K23 grant with the Research Performance Progress Report.

Data and safety monitoring activities for this study will continue until all subjects have completed their participation and until a sufficient amount of time has passed beyond which any study-related AEs are unlikely.

This protocol will be reviewed annually (at a minimum) by the Vanderbilt IRB. The goal of this process is to determine the risks and benefits of the study in the actual experience of subjects and that measures taken to minimize risks are adequate.

9.0 Study Withdrawal/Discontinuation

Subjects will be free to withdraw from the study at any time, which will be made clear at enrollment. Subjects will be withdrawn from the study if:

- Pregnancy is detected
- The PI's (or designated MD, NP, or PA KSP) medical judgement is that participation places the subject at risk for harm

10.0 Statistical Considerations

10.1 STUDY 1-7 (Aims 1-2)

10.1.1 Sample Size Justification

My accrual goal is to obtain an adequate number of participants within both the T1DM SUBSTUDY (STUDY 1-3) and CONTROL SUBSTUDY (STUDY 4-7) to ensure greater than 80% statistical power ($1-\beta$) for a two-sided α -level of 5% for each specific aim's primary outcome. The sample size calculations used the best-available previously published descriptions of insulin sensitivity(28, 105) and %FMD(7, 30, 106-108) in T1DM. Table 7 summarizes these calculations.

Table 7: Key parameters for sample size calculations for T1DM and CONTROL substudies. n , δ , $1-\beta$, σ , and r represent the sample size, the expected minimum difference, statistical power, overall standard deviation, and longitudinal correlation, respectively, for each key outcome. * indicates calculations based on preliminary data as previously described. [†] The detectable differences for GIR of 1.3 to 2.2 mg/kg/min represent a 20% to 21% change in outcomes. [‡] The detectable differences for %FMD of 2.2% to 4.3% represent a 25% to 39% change in outcomes.

Aim	T1DM Substudy					Control Substudy						
	Key Outcome for Power Calculation	n	δ	$1-\beta$	σ	r	Key Outcome for Power Calculation	n	δ	$1-\beta$	σ	r
1	GIR between STUDY T ^{LO} vs. T ^{HI} in mg/kg/min	20	1.3	0.88	2.7	0.79	GIR between STUDY C ^{BOTH} vs. C ⁰ in mg/kg/min	20	2.2	0.92	3.5	0.79
2	%FMD between STUDY T ^{LO} vs. T ^{HI}	20	2.2%	0.88	4.3%	0.83	%FMD between STUDY C ^{BOTH} vs. C ⁰	20	4.3%	0.83	3.7%	0.83

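### Three of the four powers in Table 7 do not follow from the table's own inputs, and the control %FMD power cannot be reached at any non-negative correlation

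*Combined protocol and SAP*

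**What the plan says.** Section 10.1.1 sets the accrual goal "to ensure greater than 80% statistical power" at a two-sided 5% level for each aim's primary outcome. Table 7 is offered as the summary of those calculations. Its caption defines σ and r as the "overall standard deviation, and longitudinal correlation, respectively, for each key outcome".

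The entries, in the order n, δ, power, σ, r, are:

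- T1DM GIR: "20 1.3 0.88 2.7 0.79"
- Control GIR: "20 2.2 0.92 3.5 0.79"
- T1DM %FMD: "20 2.2% 0.88 4.3% 0.83"
- Control %FMD: 20, 4.3%, 0.83, 3.7%, 0.83

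Two footnotes repeat the differences: "The detectable differences for GIR of 1.3 to 2.2 mg/kg/min represent a 20% to 21% change in outcomes" and "The detectable differences for %FMD of 2.2% to 4.3% represent a 25% to 39% change in outcomes". The section names no test, formula, software or multiplicity adjustment.

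Both contrasts are within-person. Section 6.1 has each T1DM participant attend three identical visits, and section 5.3 has each control go through STUDY 4-7 in random order. Section 10.1.3 makes clear that 20 is the number completing, after an assumed 15% dropout.

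**The concern.** With n, difference, SD and correlation all printed, the power of a paired comparison is fixed, so a reader can check it. The control %FMD row stands out: the difference exceeds the SD and the correlation is high, yet its stated power is the lowest of the four.

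These figures are the whole justification for 20 per substudy, and they state the detectable effect for the Aim 1 and Aim 2 primary comparisons. If the power column is wrong, the differences that the footnotes call detectable lie above the detection limit at the stated power. If an SD or a correlation is wrong, the true detectable difference is unknown. Section 10.1.4 also plans to examine the variance at the interim and adjust the sample size if needed. Table 7 holds the only planning SDs and correlations printed for these outcomes, so a misprint there would give that step a wrong reference.

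**Working it through.** **Method.** For a paired t-test:

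- SD of differences: SD_d = σ√(2(1 − r))
- Noncentrality: λ = δ√n / SD_d
- Power: probability that a noncentral t with n − 1 = 19 degrees of freedom and noncentrality λ falls outside ±2.093 (two-sided 5%)

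All inputs are the Table 7 entries listed above.

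**Reproducing the T1DM GIR row.** SD_d = 2.7 × √(2 × 0.21) = 1.750. λ = 1.3 × √20 / 1.750 = 3.32. Power = 0.883, against 0.88 stated. This match supports both the method and the column order.

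**All four rows.**

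| Row | δ | σ | r | SD_d | λ | Power computed | Power stated |
|---|---|---|---|---|---|---|---|
| T1DM GIR | 1.3 | 2.7 | 0.79 | 1.750 | 3.32 | 0.883 | 0.88 |
| Control GIR | 2.2 | 3.5 | 0.79 | 2.268 | 4.34 | 0.984 | 0.92 |
| T1DM %FMD | 2.2 | 4.3 | 0.83 | 2.507 | 3.92 | 0.961 | 0.88 |
| Control %FMD | 4.3 | 3.7 | 0.83 | 2.157 | 8.91 | >0.9999 | 0.83 |

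The gaps are 6, 8 and 17 percentage points.

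**Rounding of the inputs** does not explain them. Over the rounding limits, control GIR ranges from 0.975 to 0.991, T1DM %FMD from 0.943 to 0.974, and control %FMD stays above 0.9999.

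**Control %FMD at zero correlation.** SD_d = 3.7 × √2 = 5.23, λ = 4.3 × √20 / 5.23 = 3.68, power 0.936 (0.925 to 0.947 over rounding). Power rises with r, so no r ≥ 0 gives 0.83. Power of 0.83 needs λ = 3.07, that is SD_d = 4.3 × √20 / 3.07 = 6.26. That exceeds 5.23, the largest value possible for σ = 3.7 and r ≥ 0.

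**Value needed to obtain the stated power, changing one input at a time.**

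| Row | δ | or σ | or r |
|---|---|---|---|
| Control GIR (0.92) | 1.80 | 4.28 | 0.69 |
| T1DM %FMD (0.88) | 1.85 | 5.10 | 0.76 |
| Control %FMD (0.83) | 1.48 | 10.7 | -0.43 |

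For control %FMD the printed difference is 4.3 / 1.48 = 2.9 times the one that gives power 0.83 with the printed σ and r.

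**Other readings tried.** None repairs the table.

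- *Smaller α.* About 0.008 to 0.0125 would fit control GIR, and about 0.0125 to 0.0167 would fit T1DM %FMD. Both contradict the stated 5%, and they take the T1DM GIR row down to 0.65-0.75.
- *Smaller n.* Control GIR fits at n = 14 (0.918) and T1DM %FMD at n = 15 (0.884), but the T1DM GIR row needs n = 20. Control %FMD goes from 0.75 at n = 4 to 0.91 at n = 5, so no whole number gives 0.83.
- *σ read as the SD of the difference.* Control GIR 0.760, T1DM %FMD 0.584, control %FMD 0.998.
- *Independent groups.* Control %FMD gives 0.947 with 20 per group and 0.691 with 10 per group.
- The normal approximation, one-sided testing, ANCOVA, two-group change scores, residual-SD variants and interchanging the table's δ and σ values were also tried. None reproduces all four rows.

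**The case against.** The strongest reply is that every discrepancy is conservative. The only target is power above 80%. All four stated powers meet it, and on the printed inputs the three disputed rows exceed it by more than claimed. If the power column is simply out of date, design, conduct and analysis are unchanged. This stands: the point is not that the trial is underpowered. It does not rescue the table, because the documents do not show whether a power or an input is wrong.

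Second, the method is inferred, since section 10.1.1 names no test and section 10.1.2 plans regression. That is fair, and the statement about non-negative correlations applies to a paired comparison with n = 20 at a two-sided 5% level. However, the table supplies the inputs of a paired calculation, and one row reproduces under it to two decimals. The table should agree with itself whatever model is fitted later.

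Third, the table may have been damaged in conversion from PDF, or a cell may be duplicated: power and r are both 0.83 in the control %FMD row, and the footnotes confirm only the differences. This cannot be excluded for that row. It would not explain control GIR or T1DM %FMD, and each row still splits into two complete sets of five values.

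Finally, the 2.9-fold figure takes the row's power, σ and r as correct. It measures the inconsistency and does not estimate the true detectable effect.

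**Conclusion.** The concern holds. Under a paired t-test with 20 completers at a two-sided 5% level, the powers that follow from Table 7 are 0.88, 0.98, 0.96 and above 0.99. Table 7 states 0.88, 0.92, 0.88 and 0.83. Three are understated, by 6, 8 and 17 points, and the control %FMD power cannot be obtained at any non-negative correlation. At least one entry in each of the three rows is therefore misreported, and the documents do not allow a reader to tell which.

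The printed inputs satisfy the 80% target, so no loss of power is shown. What fails is the check on the basis for n = 20, most seriously for %FMD, where both rows are inconsistent. The conclusion rests on σ being the SD of the outcome and r the within-person correlation, as the caption defines them, and on the table cells being as printed.

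**What to change.** Name the test, formula and software behind Table 7 and recompute all four rows in the same way. Then take whichever course applies:

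- If the inputs are right, change the three powers to 0.98 (control GIR), 0.96 (T1DM %FMD) and above 0.99 (control %FMD). State whether δ is an expected or a minimum detectable difference, since the caption and the footnotes describe it differently.
- If the powers are right, replace the wrong δ, σ, r or n with the value actually used and give its source.

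In either case, bring the detectable differences and percentages in the two footnotes into line.

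The cost is a revision of one table and its footnotes. If only the powers were wrong, 20 per substudy stands. If an SD, correlation or difference was wrong, confirm that 20 completers still give more than 80% power before relying on it, and use the corrected values as the reference for the interim variance review in section 10.1.4.

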10.1.2 Analysis Plan

The correlation between the independent variable TDD_{insulin} (averaged over 7 days prior to each STUDY visit) and the key dependent variable for each objective will be determined: GIR in Aim 1; %FMD and MVR in Aim 2. Several other explanatory variables could influence each specific aim's key dependent variable, however. For example, confounding variables might include hyperglycemia, hyperlipidemia, or the dependent variables in each aim could affect one another (e.g. insulin resistance could affect endothelial dysfunction). For this reason, I will use multivariable linear regression analysis to account for the effect of potential confounders, which include age, T1DM duration, glycemia (both from both CGM over 7 days and HbA1c), lipidemia (i.e. lipoprotein subclass sizes and particle concentrations), NEFA concentration, hypertension, BMI, body composition, and estrogen level.

The study accrual of 40 participants provides 3 to 4 degrees of freedom for a multivariable linear regression analysis. (i.e. TDD_{insulin} and 3 additional independent variables can be included in an adequately-powered model). To quantify the effect of potential confounders, unadjusted and adjusted linear regression models will be fit and compared for each Aim's primary outcome (GIR and %FMD). I will analyze changes in β -coefficients between unadjusted and adjusted models for scientifically significant differences.

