To test this hypothesis, I will analyze the relationship (figure 1) between hyperinsulinemic exposure (quantified by average total daily dose of insulin, $TDD_{insulin}$) and insulin sensitivity (Aim 1) and early endothelial dysfunction (Aim 2) at multiple points in the progression of T1DM (figure 2). In a longitudinal study (T1DM SUBSTUDY in figure 2), I will study patients at three phases over the 12 months following diagnosis, initial diagnosis, honeymoon phase, and post-honeymoon phase. Each phase has distinct insulin exposure: 1) soon after diagnosis (STUDY1: $TDD_{insulin} \approx 0.5$ units/kg/day), 2) during partial clinical remission (PCR), a.k.a. "Honeymoon phase" (STUDY2: $TDD_{insulin} < 0.4$ units/kg/day), and 3) after emergence from PCR (STUDY3: $TDD_{insulin} > 0.6$ units/kg/day). Additionally, we will study healthy, matched, euglycemic control participants to assess the contribution of hyperinsulinemia to IR under four experimental conditions (CONTROL SUBSTUDY in figure 2): (i) endogenous insulin only (STUDY 4), (ii) overnight hyperinsulinemia (IV insulin infusion, STUDY 5), (iii) one week of mild hyperinsulinemia (glargine, STUDY 6), and (iv) both overnight insulin and one week of hyperinsulinemia (STUDY 7). To further test this hypothesis, I will conduct a 2x2 crossover intervention study in adults with T1DM testing whether the reduction in $TDD_{insulin}$ associated with a one-week, isocaloric low-carbohydrate diet (LCD) intervention will result in improved insulin sensitivity compared with one-week, isocaloric, standard carbohydrate diet (SCD) (STUDY B-C, figure 3).

T1DM SUBSTUDY (n=20)

CONTROL SUBSTUDY (n=20)

[figure not shown]

Figure 2: Schematic for STUDY visits. Est. = estimated.

PCR=partial clinical remission. $TDD_{insulin}$ = total daily dose of insulin

Specific Aim 1: Quantify the contribution of iatrogenic hyperinsulinemia to IR during the early course of T1DM. The hyperinsulinemic, euglycemic clamp technique will quantify insulin sensitivity at each STUDY visit. Although insulin sensitivity improves during PCR,(28) no study to date has determined how much iatrogenic hyperinsulinemia contributes to reduced insulin sensitivity during this time.

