7.1 Hyperinsulinemia

The hyperinsulinemic, euglycemic clamp exposes participants to high insulin levels, potentially leading to hypoglycemia and hypokalemia. As shown in figures 6 and 8, the insulin infusion rate during the clamp will be 40 mU/m²/min. This infusion rate is anticipated to result in plasma insulin concentrations between 50 and 130 μ U/mL,(64, 65) levels that are within the range of physiological hyperinsulinemia and comparable to concentrations seen after meal ingestion.(65-67) By comparison, the most commonly used insulin infusion rate in the treatment of diabetic ketoacidosis is 0.1 U/kg/hr.(56) In a 70 kg, 1.73 m² individual, this infusion rate would equal 67 mU/m²/min, over 50% higher than the 40 mU/m²/min rate used in this study.

Nondiabetic CONTROL SUBSTUDY participants will be exposed to low levels of iatrogenic hyperinsulinemia from low doses of insulin glargine (STUDY 6-7)

and overnight IV regular insulin infusions prior to STUDY visits (STUDY 5 and 7). The insulin glargine dose of 0.2 u/kg/day was selected to induce long-term (7 days) iatrogenic hyperinsulinemia while avoiding the confounding effect of hypoglycemia. Based on a previous pharmacokinetic-pharmacodynamic study of glargine, this dose is anticipated to drop fasting plasma glucose by no more than 10 mg/dL.(68) Because insulin glargine is a long-acting insulin analog, we do not anticipate it will cause a rapid drop in plasma glucose concentrations, but rather a slow decrease over the course of hours. For short-term hyperinsulinemia, participants will receive intravenous (IV) regular insulin at 8 mU/m²/min for 8 hours overnight preceding the STUDY visit. Based on my previous research, I anticipate this dose will raise fasting plasma insulin concentrations in CONTROL SUBSTUDY participants from ≈8 µU/mL to ≈21 µU/mL, matching the average fasting insulin concentration of T1DM SUBSTUDY participants.(69)

We will use the following safety provisions to minimize risk of hypoglycemia and hypokalemia:

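### In Aims 1-2 the only exposure is insulin dose averaged over 7 days, so the planned regression cannot isolate the effect of the control substudy's overnight insulin infusion

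*Combined protocol and SAP*

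**What the plan says.** Section 2.0 defines "hyperinsulinemic exposure (quantified by average total daily dose of insulin" as the quantity to be related to insulin sensitivity and endothelial function. It also sets out four control conditions: endogenous insulin only (STUDY 4), "ii) overnight hyperinsulinemia (IV insulin infusion, STUDY 5), (iii) one week of mild hyperinsulinemia (glargine, STUDY 6", and both together (STUDY 7). This is a 2x2 layout within each person.

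Section 7.1 gives the two exposures. Controls receive "regular insulin at 8 mU/m²/min for 8 hours overnight preceding the STUDY visit", expected to raise fasting insulin "from ≈8 µU/mL to ≈21 µU/mL, matching the average fasting insulin concentration of T1DM SUBSTUDY participants". For the week-long exposure: "The insulin glargine dose of 0.2 u/kg/day was selected to induce long-term (7 days) iatrogenic hyperinsulinemia".

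Section 10.1.2 (Analysis Plan, under the STUDY 1-7 heading) correlates one independent variable, TDD, "averaged over 7 days prior to each STUDY visit) and the key dependent variable for each objective will be determined". It then fits unadjusted and adjusted linear regressions. The listed confounders include neither the assigned control condition nor plasma insulin. The section counts 40 participants when it sets the model's degrees of freedom, so both substudies are in the regression.

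Table 7 powers the control substudy on the both-versus-none contrast (C-BOTH versus C-0). Section 10.1.2 does not mention that contrast.

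**The concern.** The overnight infusion is one of the two things the control substudy manipulates, and it is sized to reproduce the fasting insulin level of T1DM participants. It lasts one night. Averaging dose over a week dilutes it to almost nothing beside seven daily glargine injections. STUDY 4 and STUDY 5 then have nearly the same exposure value, although the protocol expects plasma insulin of about 8 and about 21 µU/mL at those visits.

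At stake is whether the written plan can say anything about short-term hyperinsulinemia as distinct from week-long hyperinsulinemia. The same coding is used for both primary outcomes, GIR and %FMD.

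**Working it through.** **Unit check.** Section 7.1 converts 0.1 U/kg/hr at 70 kg and 1.73 m² to 67 mU/m²/min. Recomputed: 0.1 × 70 × 1000 / 60 / 1.73 = 67.4. The same body size is used below.

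**Exposure value of each control condition**
- Overnight dose: 8 mU/m²/min × 1.73 m² × 480 min = 6,643 mU = 6.64 U.
- As a 7-day mean: 6.64 / 70 / 7 = 0.0136 U/kg/day.
- Glargine: 0.200 U/kg/day. Ratio: 0.0136 / 0.200 = 6.8%.
- Assumed body sizes from 50 kg/1.5 m² to 95 kg/2.15 m² give 8.2% to 6.2%. A 10-hour infusion at 50 kg gives 10.3%.
- TDD for STUDY 4, 5, 6, 7: 0, 0.0136, 0.2000, 0.2136. If clinic IV insulin is not counted: 0, 0, 0.2, 0.2.

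**What TDD measures among controls.** In a balanced 2x2, the correlation of TDD with the overnight factor is 0.0136 / √(0.0136² + 0.2²) = 0.07. With glargine it is 0.2 / √(0.0136² + 0.2²) = 0.998. Among controls, TDD is in effect a glargine indicator.

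**Control-only fit, equal split of Table 7's 2.2 mg/kg/min.** Condition effects on GIR are 0, −1.1, −1.1, −2.2.
- Mean TDD 0.1068; sum of squared deviations 0.0402; sum of cross-products −2 × 0.1068 × 1.1 = −0.235.
- Slope = −0.235 / 0.0402 = −5.85 mg/kg/min per U/kg/day.
- STUDY 5 versus 4: fitted 5.85 × 0.0136 = 0.08, true 1.1.
- STUDY 6 versus 4: fitted 5.85 × 0.2 = 1.17, true 1.1.
- STUDY 7 versus 4: fitted 1.25, true 2.2. Correlation of condition means with TDD: −0.75.

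**Control-only fit, whole effect overnight.** Effects are 0, −2.2, 0, −2.2. The slope is −0.74, fitted STUDY 7 versus 4 is 0.16, and the correlation is −0.07.

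**Pooled fit, closer to the 40-participant plan (illustration).**
- Assumed T1DM TDD: 0.35, 0.50 and 0.65, within the Section 2.0 and 6.1 bands.
- Assumed T1DM GIR: 6.5, 5.85 and 5.2. The top value is 1.3 / 0.20 from Table 7's footnote.
- Assumed control GIR: 10.5 without overnight insulin (2.2 / 0.21) and 8.3 with it, so the whole effect is overnight.
- Across the seven condition means, the slope is −7.5 and the correlation −0.85. STUDY 5 versus 4 is fitted as 0.10, true 2.2.

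**Precision of a factor model.** From Table 7's SD of 3.5, correlation of 0.79 and n = 20, assuming equal correlation across the four visits:
- Within-person SD = 3.5 × √0.21 = 1.60.
- Each main effect: 1.60 / √20 = 0.36.
- Both-versus-none: 1.60 × √(2/20) = 0.51.
- Interaction: 2 × 1.60 / √20 = 0.72.

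As printed, the control GIR inputs give power of 0.98 in a paired t test, against the stated 0.92. A table damaged in extraction may explain this, so these standard errors are provisional.

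**The case against.** The strongest reply is that a dose-response relation would still be reported. That is largely right. A reader might infer that the plan would find no link between insulin and resistance even though the conditions differ, or that over 90% of the effect would be lost (0.16 fitted of 2.2). The documents do not support that. It requires the whole effect to be overnight and a control-only regression that Section 10.1.2 does not describe. With an equal split, even the control-only fit gives a correlation of −0.75. In the pooled illustration the correlation is about −0.85 in the worst case, mostly as a difference between T1DM and control groups. What remains is that the overnight effect is not isolated in any of these fits.

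A second reply is that Table 7 names both-versus-none as the key control outcome, and this includes the overnight exposure at full size. That is true, but the contrast cannot separate the two factors and is not carried into Section 10.1.2.

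Third, leaving endogenous insulin out of TDD might look like another defect. It is not, because the hypothesis concerns iatrogenic insulin, and basal insulin and C-peptide are drawn (Table 3).

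Finally, the factor model's smaller main-effect standard error is not a gain in power over both-versus-none. Under an equal split the ratios are 1.1 / 0.36 = 3.1 and 2.2 / 0.51 = 4.3. The case for the factor model is that it answers the separate question.

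**Conclusion.** The point holds as a limit on what the regression can estimate. With 7-day TDD as the only exposure, a linear model sets the overnight effect at about 7% of the glargine effect (6% to 10% across the body sizes and durations tried), or at zero if clinic IV insulin is excluded. Under an equal split, the control-only fit assigns 0.08 mg/kg/min to an effect of 1.1.

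The dose arithmetic rests on the protocol's own rate, duration and body size. The GIR figures depend on an assumed split of Table 7's 2.2, and the pooled figures also on assumed TDD and GIR levels. No claim is made that an overall relation would be missed.

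Section 5.3 gives the one-week condition as STUDY 5 and the one-night condition as STUDY 6, the reverse of Sections 2.0, 6.1 and 7.1. These must be reconciled before conditions are coded; the calculation does not depend on the labels.

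**What to change.** In Section 10.1.2:

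1. Add for STUDY 4-7 a within-participant model of GIR and of %FMD on overnight insulin (yes/no), glargine (yes/no) and their interaction. Make it the basis for conclusions about the control conditions.
2. Add measured basal plasma insulin (Table 3) as a supporting continuous exposure.
3. State whether IV insulin given in the clinic counts towards TDD.
4. State that the TDD slope will not be used to judge the overnight condition.

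The pooled TDD model can stay beside this. The cost is a little more analysis, with no new visits or assays. The interaction will be imprecise: a standard error of about 0.72 mg/kg/min, against about 0.36 for each main effect, assuming equal correlation across visits.

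If controls are instead removed from the TDD model, 20 T1DM participants remain. By the rule of 10 participants per degree of freedom in Section 10.2.1, that supports 20 / 10 = 2 degrees of freedom, and the three to four stated in Section 10.1.2 must be revised.
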